IBM SPSS Statistics for Windows (version 25, IBM Corp, Armonk, NY, USA) will be used for descriptive analyses. First, the intervention group and control group will be compared on their sociodemographic characteristics by use of Pearson's chi-square tests and independent samples t-tests. Second, mean scores on the various determinants will be calculated. Third, change scores (i.e., the difference in mean score between the baseline measurement and the follow-up measurements) will be calculated. Linear mixed model analyses will be used to assess the longitudinal effect of the intervention on the various determinants assessed in the questionnaire, as this method corrects for correlation within individuals within groups, which occurs in repeated-measures research designs. Another advantage of this technique is that it naturally handles missing values, in case data are missing at random. Since measurements will be repeated within participants, who are nested within classes, we will use a three-level model with classes as third level, participants as second level and measurements as first level. The fixed part of the model consists of group (intervention versus control), time (time-points at which the measurements are taken) and the interaction term group*time. Baseline variables that are related to missing data and/or outcome will also be included to obtain unbiased results and/or to gain precision. As for the random part of the model, a random intercept on class level will be included next to an unstructured covariance structure for the repeated measurements. Relative effect sizes will be calculated for each determinant. These will be expressed as Cohen's d: a Cohen's d of 0.2 is interpreted as a small, 0.5 as a medium and 0.8 as a large effect size (8). Results will be interpreted as significant when $p < 0.05$ (two-sided).

Data Storage

The anonymised data from the questionnaires will be stored and transported in accordance with the Maastricht University Data Management Guidelines (Table 1 and 2). All data will be kept fifteen years after data-collection (GCP) and ten years after publication of the results in a peer-reviewed journal, unless a participant requests otherwise as stated in article 455 book 7 of the Civil law book (in Dutch: Burgerlijk Wetboek).

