After the T2 measurement, the envelopes with filled-in questionnaires are collected by Kids University for Cooking BV (intervention group) or researchers (control group). The envelopes with the ID number and name of the child, in which the blank questionnaires were stored, are not collected and will remain at the school. This means that only anonymised data will be collected, all non-anonymised data (envelopes with ID number and child's name) will remain at school. Researchers therefore only have access to the anonymised data. All anonymised data will be delivered to the principal researcher at Maastricht University.

In the data analyses, the mean scores of the answers on the questions will be used. Since single unrelated questions will be asked to test different aspects of knowledge, a score of correct answers will be used in further analyses of this determinant.

Data will quantitatively be analysed using IBM SPSS Statistics for Windows (version 25, IBM Corp, Armonk, NY, USA). Numerical variables will be presented as mean \pm standard deviation (SD), where number (%) will be used for categorical variables. A two-tailed test is considered statistically significant with p-values ≤ 0.05 . Questionnaire items for the determinants knowledge, intention, attitude, skills and taste preferences are combined into one variable per determinant for each time point. Differences in numerical baseline parameters between the control and intervention group will be tested with the independent-samples t-test or Mann-Whitney U-test where appropriate, while the Chi-square test, or Fisher's exact test, will be used for categorical variables. To investigate the in-

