participants' knowledge. In 2014, Kasten et al. performed a one-group effect evaluation of the Kokkerelli Learning Street (10). In this study, the outcome measure that changed most significantly was the determinant knowledge (mean difference T2-T0: 0.41, SD: 0.93). However, this study did not include a control group and the outcomes therefore only indicate within-group differences instead of between-group differences, while the present study does include a control group. The following assumptions were used for the sample size calculation:

- Children are nested within school classes, with 25 participants per class, and seven intervention classes and seven control classes;
- A significance level (alpha) of 0.05;
- A power of 80%;
- Independent samples t-test on difference in knowledge scores;
- An Intraclass Correlation Coefficient of 0.04, based on values used by Battjes et al. (8);
- A dropout rate of 10%, as based on dropout rates observed by Bartelink et al. (12);
- An SD of 0.24 for the mean change in absolute knowledge score (T2-T0) in the population, as based on the effect evaluation of a comparable programme by Battjes et al. (8).

With these assumptions, we can demonstrate an effect size of 0.104 on absolute knowledge scores. The standardised effect size is then equal to $0.104/0.22 = 0.47$, indicating a small to medium effect size (11).

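### Baseline comparisons use child-level tests that ignore classes, so their p-values are too small for any variable that clusters by class (about 16% rejection instead of 5% if the knowledge ICC of 0.04 applied)

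*Combined protocol and SAP*

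**What the plan says.** The baseline comparison is described twice.

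- Section 1.2, Data Processing and Statistical Analyses, for numerical variables: "Differences in numerical baseline parameters between the control and intervention group will be tested with the independent-samples t-test or Mann-Whitney U-test where appropriate". For the rest: "while the Chi-square test, or Fisher's exact test, will be used for categorical variables". The same paragraph sets a general two-sided criterion of 0.05 ("A two-tailed test is considered statistically significant with p-values" at or below that value) and plans mean and SD, or number and percentage, as descriptive summaries.
- Reply to the committee of 21-11-2019, same heading: "the intervention group and control group will be compared on their sociodemographic characteristics by use of Pearson's chi-square tests and independent samples t-tests".

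Neither place attaches a class term or any clustering correction to these tests. The reply limits them to sociodemographic variables. Section 1.2 speaks of baseline parameters without listing them, so the baseline scores on the determinants may be included.

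Elsewhere the plan does treat classes as clusters. Section 1.6 assumes: "Children are nested within school classes, with 25 participants per class, and seven intervention classes and seven control classes". It also assumes: "An Intraclass Correlation Coefficient of 0.04". The effect model, in section 1.2 and in the reply, has three levels with a random intercept for class.

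**The concern.** Children are not assigned to arms one by one. The intervention arm consists of the year-five classes that take part in the Learning Street for the first time, and the control arm consists of classes from schools in the larger study. A t-test, Mann-Whitney, chi-square or Fisher test on roughly 350 children (14 classes of 25) takes the variance of the arm difference as if there were 350 independent observations. If children in the same class resemble each other on the variable tested, that variance is too small and so is the p-value.

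What is at stake is the reported baseline comparison. The study is non-randomised and controls are matched only where possible, so readers will look at it closely. With the 0.05 criterion applied, a variable could be reported as differing significantly between the arms when ordinary variation between classes accounts for the difference.

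**Working it through.** **Inputs.** All are from section 1.6: 25 children per class, 7 + 7 classes, ICC 0.04, two-sided alpha 0.05, power 80%, dropout 10%, SD 0.24 for the change in knowledge. The documents give no error rate for the baseline tests and no ICC for any baseline variable.

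**Step 1: reproduce the plan's own figure.** Section 1.6 states a detectable difference of 0.104.

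- After dropout, children per class: m = 25 × 0.9 = 22.5. Children per arm: n = 7 × 22.5 = 157.5.
- Design effect: DE = 1 + (m − 1) × ICC = 1 + 21.5 × 0.04 = 1.86.
- Effective n per arm: 157.5 / 1.86 = 84.7.
- Detectable difference: (1.960 + 0.842) × 0.24 × √(2 / 84.7) = 0.103 by the normal approximation, or 0.104 with the t distribution.

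Without the design effect the same formula gives 2.802 × 0.24 × √(2 / 157.5) = 0.076. The stated 0.104 therefore does incorporate class clustering at ICC 0.04.

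**Step 2: rejection rate of a test that ignores classes.** With DE = 1 + (m − 1) × ICC, the true standard error is √DE times the one the child-level test uses. With no true difference between the populations of classes, the two-sided rejection rate of a nominal 5% test is 2 × [1 − Φ(1.96 / √DE)].

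At baseline, with m = 25 and ICC = 0.04:

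- DE = 1 + 24 × 0.04 = 1.96 and √DE = 1.40.
- 1.96 / 1.40 = 1.40, and 2 × [1 − Φ(1.40)] = 16.2%.

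With 22.5 per class (DE 1.86) the rate is 15.1%.

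**Step 3: range over the ICC, m = 25.** All ICC values are assumed as far as the baseline variables are concerned.

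| ICC | Design effect | Rejection rate |
|---|---|---|
| 0 | 1.00 | 5.0% |
| 0.01 | 1.24 | 7.8% |
| 0.02 | 1.48 | 10.7% |
| 0.04 | 1.96 | 16.2% |
| 0.05 | 2.20 | 18.6% |
| 0.10 | 3.40 | 28.8% |

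**Step 4: check by simulation.** With 7 + 7 classes of 25, ICC 0.04 and no true difference, the t-test rejected 16.2% of the time, Mann-Whitney 16.1%, and chi-square 15.8% to 16.3% for prevalences between 0.10 and 0.50. Fisher's exact test was not simulated. A t-test on the class means rejected 5.0% of the time.

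**The case against.** **The ICC is borrowed.** The 0.04 belongs to the knowledge sample size. A reader might infer that 16% is the error rate of every planned baseline test on the plan's own figures. The documents do not support that: they give no ICC for age, gender, birth country or the other determinants. All children are in year five, which restricts age, and gender need not cluster by class at all. This stands, and it is why the range above starts at 5%. Higher values are also possible. The questionnaire concerns one of nine food products, and if products differ between classes, baseline knowledge and taste could cluster more strongly. That too is inference.

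**Nothing else depends on these p-values.** A reader might infer that the inflation carries over to the choice of covariates or to the effect test. It does not. Covariates enter by their relation to missing data or outcome, and the effect model has a random class intercept. This stands and limits the importance of the point.

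**The tests are not called proof of comparability.** A reader might take them as the plan's stated evidence that the arms are comparable. The text says only that differences will be tested or groups compared. What it offers against confounding is matching where possible and covariate adjustment. This stands as well.

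**Part of the remedy is already planned.** Descriptive summaries are in section 1.2. If T0 is one of the time points in the mixed model, as the wording suggests, that model also gives a class-adjusted contrast at T0 for the determinants. It does not do so for the demographic variables, and the separate child-level tests remain as written.

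**The error leans towards caution.** Flagging too many imbalances is less harmful than missing them, and an imbalance that arises from classes is still a real imbalance between the children compared. That is fair, but it is a reason to report the size of the imbalance rather than a miscalibrated p-value.

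**Conclusion.** The baseline tests are wrong as written. They assume independent children where whole classes form the arms, and they are out of step with the plan's own sample size and effect model. For a variable with the ICC that section 1.6 uses for knowledge, the rejection rate with no true difference would be about 16% rather than 5%. For other variables the rate is unknown: it stays at 5% without clustering, is about 8% at ICC 0.01 and 11% at 0.02, and reaches 29% at 0.10. These figures assume 25 children in each class.

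This is a minor point. It affects the p-values in the baseline comparison and how they are read, and gives no ground for doubting the effect estimate or its test.

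**What to change.** In the Data Processing and Statistical Analyses text of both section 1.2 and the reply of 21-11-2019:

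- Keep the planned mean (SD) and number (%) by arm.
- Replace the baseline significance tests with standardised differences between the arms.
- If p-values are kept, take them from a class-level comparison (for example a t-test on the 14 class means or class proportions) or from a linear or logistic mixed model with a random class intercept.

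The cost is a few sentences and slightly different table entries. No new data, change in sample size or change to the effect analysis is needed.

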Rationale: From 2015-2020, the 'Healthy Primary School of the Future' intervention took place in Parkstad. The school environment of four primary schools changed. Two schools became 'Healthy Primary Schools of the Future'; providing their students with a healthy lunch and structured physical activity (PA) sessions during lunch time breaks. Two other 'Physical Activity Schools' only implemented the structured PA sessions. METC Z previously decided that this study falls under non-WMO guidelines (METC-Z no. 14-N-142). Interim analyses showed promising effects of the intervention; at two-year-follow-up, the study showed a significant decrease in BMI z-score of children in the 'Healthy Primary Schools of the Future' as compared with children in control schools. Also, positive intervention effects on dietary and PA behaviours were observed. Following these promising results, childcare centres of educational board Prisma have expressed their interest in implementing changes fitting the 'Healthy Primary School of the Future' initiative. However, this is more complex than it seems to be, as budget to implement changes is lower than in the original trial, and all childcare centres have a unique context. Therefore, there is a need to investigate how 'Healthy Primary School of the Future' can successfully be implemented in various, real-life school-settings. It is hypothesised that to maximise implementation and sustainability, each childcare centre will need to put together a set of changes and interventions which fit the context and needs of all stakeholders involved (e.g., the school board, teachers, parents and children).

Objective: The main objective is to study the implementation process of 'Healthy Childcare Centre of the Future' in different school-contexts and develop guidelines that can be used to facilitate widespread dissemination of the initiative. Secondary objectives include evaluating the effects of the 'Healthy Childcare Centre of the Future' on children's BMI z-score, general health, dietary and PA behaviours and school well-being. To reach these objectives, a process evaluation, effect evaluation and cost-effectiveness evaluation will be executed.

Study design: A non-randomised, non-controlled, observational study design.

Study population: Children in study years four to six (at baseline) of twelve childcare centres located in Limburg.

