1.2 What are the methodologies that you will employ in the study?

Study Design

A non-randomised, pre-test post-test controlled trial will be conducted to answer the research questions. The participants in the intervention group will participate in the Learning Street, while the control group receives no intervention and continues with their regular curriculum. None of the participants is subjected to an intervention as part of this study, as children in the intervention group would also have participated in the Learning Street if the present study would not have taken place. The trial is non-randomised, as the intervention group consists of all study years five who participated in the Learning Street for the first time during school year 2019-2020.

School classes in the control group will be waived from a pool of primary schools already participating in a larger study. This larger study examines the implementation process of various health-promoting initiatives at primary schools. As this study is a process evaluation, no intervention is imposed but the implementation process is followed. Schools participating in this research are free to choose if, when and how they want to implement health-promoting initiatives in their school context. Some schools participating in this research are not planning to implement any health-promoting initiatives any time soon. Therefore, these schools can serve as control schools in the present study, as they will continue with their regular curriculum for the duration of the present study. In these control schools, children from study year five and their parents will be informed about the larger study, including the measurements that will be used for the present study. Subsequently, they are asked to give their consent for their child to participate in the study. Where possible, the control schools are matched to the intervention school classes with regard to potential confounders such as school location and number of students.

Participants

Participants are students from study year five (age 8-10 years) of primary schools located in Northern Limburg, the Netherlands. Researchers and employees of Kids University for Cooking BV will inform children about the study. Information brochures are distributed and parents are asked to give permission for their children to participate in the study. Informed consent will be obtained from all parents of participating children.

Kokkerelli Learning Street

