tervention effect on children's determinants, mean scores on the various determinants will be calculated. Then, change scores (i.e., the difference in mean score between the baseline measurement and the follow-up measurements) will be calculated. Linear mixed model analyses will be used to assess the longitudinal effect of the intervention on the various determinants assessed in the questionnaire, as this method corrects for correlation within individuals within groups, which occurs in repeated-measures research designs. Another advantage of this technique is that it naturally handles missing values, in case data are missing at random. Since measurements are repeated within participants, who are nested within classes, we use a three-level model with classes as third level, participants as second level and measurements as first level. The fixed part of the model consists of group (intervention versus control), time (time-points at which the measurements are taken) and the interaction term group*time. Baseline variables that are related to missing data and/or outcome will also be included to obtain unbiased results and/or to gain precision. As for the random part of the model, a random intercept on class level will be included next to an unstructured covariance structure for the repeated measurements. Relative effect sizes will be calculated for each determinant. These will be expressed as Cohen's d: a Cohen's d of 0.2 is interpreted as a small, 0.5 as a medium and 0.8 as a large effect size (11).

1.3 How will humans be participants in the study (either directly or indirectly, for example, through the use of their personal data)?

All children from the intervention and control classes whose parents have given their consent are asked to fill in the questionnaires. Only anonymised data will be collected and used in the present study.

1.4 Does your study re-use data that has already been gathered for another project or purpose? If so, do you have permission to re-use that data, and was there the relevant consent for this re-use in the first study? (Please explain, with reference to, for example, previous ethics committee decisions and informed consent protocols.)

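### The mixed model and the sample size stop at class; if any school supplies two or more classes and changes differ between schools, the standard error of the group effect is too small

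*Combined protocol and SAP*

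**What the plan says.** Section 1.2 (Data Processing and Statistical Analyses) sets out a linear mixed model: "we use a three-level model with classes as third level, participants as second level and measurements as first level". On the random side, "a random intercept on class level will be included next to an unstructured covariance structure for the repeated measurements". On the fixed side, "The fixed part of the model consists of group (intervention versus control), time (time-points at which the measurements are taken) and the interaction term group*time". The reply to the committee of 21-11-2019 describes the same model. Neither text contains a school term.

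Section 1.6 uses the same top level: "Children are nested within school classes, with 25 participants per class, and seven intervention classes and seven control classes", with a single ICC of 0.04. It gives no number of schools, no school-level ICC and no limit of one class per school.

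Section 1.2 (Study Design) decides control eligibility by school: "Some schools participating in this research are not planning to implement any health-promoting initiatives any time soon", and those schools may act as controls. Then "In these control schools, children from study year five and their parents will be informed about the larger study", which reads as the year group rather than one chosen class. The reply of 13-01-2020 describes the larger study that supplies the controls: "Children in study years four to six (at baseline) of twelve childcare centres located in Limburg". The intervention arm is defined as every year-five group taking part in the Learning Street for the first time in 2019-2020.

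**The concern.** Parallel classes in one school share a building, a neighbourhood, a school policy and often staff. If their knowledge scores change together for those reasons, two classes from one school carry less information than two classes from different schools. A model whose top level is class counts them as independent. The group effect then looks more precise than it is, and a test planned at "A significance level (alpha) of 0.05" (two-sided) rejects too often. The detectable difference in 1.6 also rests on 14 independent clusters.

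Shared schools are plausible here. Seven control classes are needed and only some schools in a twelve-centre study qualify. If fewer than seven qualify, at least one must supply two classes. In the intervention arm, nothing excludes two parallel year-five classes from one school.

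**Working it through.** **Inputs from section 1.6.** Seven classes per arm, 25 children per class, 10% dropout, ICC 0.04, SD of the T2-T0 change 0.24, power 80%, alpha 0.05 (two-sided by section 1.2).

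**Assumed, because the documents do not say.** The number of classes each school supplies (c), and the part r of the 0.04 ICC that lies at school level: half (0.02) or all (0.04). As in 1.6, the ICC is taken to apply to the change score.

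**1. The plan's own figure.** Children analysed per class: 25 × 0.9 = 22.5. Design effect: 1 + 21.5 × 0.04 = 1.86. Effective n per arm: 7 × 22.5 / 1.86 = 84.7. Detectable difference: 2.80 × 0.24 × √(2/84.7) = 0.103 by the normal formula, and 0.1039 by a noncentral t on effective N minus 2 degrees of freedom. The stated 0.104 is therefore reproduced with class as the only cluster.

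**2. Adding school.** The variance of one arm's mean change is

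0.24² × [0.96/157.5 + (0.04 − r)/7 + r × Σc²/49], with 157.5 = 7 × 22.5.

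- One class per school: Σc² = 7, so r drops out. The bracket is 0.006095 + 0.005714 = 0.011810, and the SE of the difference is √(2 × 0.0576 × 0.011810) = 0.0369.
- Classes 2+2+2+1 from four schools: Σc² = 13. With r = 0.02 the bracket is 0.006095 + 0.002857 + 0.005306 = 0.014258; with r = 0.04 it is 0.006095 + 0.010612 = 0.016707. With both arms like this, the SE is 0.0405 or 0.0439, which is 1.10 or 1.19 times the planned SE.
- One school with two classes, five with one: Σc² = 9. With both arms like this, the SE is 0.0381 or 0.0394, a ratio of 1.03 or 1.07.
- Control arm 2+2+2+1, intervention arm one class per school: the SE is 0.0388 or 0.0405, a ratio of 1.05 or 1.10.

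**3. Effect on the test.** A class-level test also underestimates its own SE, because classes from one school resemble each other and so spread less. With 2+2+2+1 and r = 0.04, the expected variance among class means, in units of SD², is 0.96/22.5 + 0.04 × (49 − 13)/42 = 0.07695. Divided by 7 this is 0.01099, against a true 0.01671. The true SE is √(0.01671/0.01099) = 1.23 times the estimated one.

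Simulated type I error of a class-level t-test of change (12 df, nominal 5%):

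| Classes per school | r = 0.02 | r = 0.04 |
|---|---|---|
| One per school, both arms | 5% | 5% |
| One school per arm supplies two | 5.7% | 6.6% |
| Control arm only, 2+2+2+1 | 6.3% | 7.7% |
| Both arms, 2+2+2+1 | 7.6% | 10.7% |

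**4. Detectable difference on cluster-based degrees of freedom.** The approximation is (t at 0.975 + t at 0.80) × SE.

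- One class per school, 12 df: (2.179 + 0.873) × 0.0369 = 0.113.
- Four schools per arm, 6 df: (2.447 + 0.906) × 0.0405 = 0.136, or × 0.0439 = 0.147. The noncentral t gives 0.137 and 0.148.
- Four schools per arm, 6 df, with no school variance at all: 0.124 by the noncentral t. Part of the increase is therefore due to the lost degrees of freedom alone.

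**The case against.** The strongest reply is that the harm needs two facts that the documents never state: a school with more than one participating class, and variation between schools in change. This stands. The word for how many schools qualify gives no number and does not rule out seven or more of twelve. Matching control schools to intervention classes, as section 1.2 describes, is compatible with one class per school.

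A reader might also infer that schools are the units of entry in both arms. The text supports this only for control eligibility. The intervention arm is described by year groups and classes, and the reply of 21-11-2019 speaks of control classes being chosen and matched. The rows with shared schools in both arms are therefore further from the evidence than the control-only row. Placing all of the ICC at school level is also an extreme: teachers deliver two of the lessons and supervise the questionnaires, so some class-level variation is to be expected.

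Finally, the error rates belong to a class-level t-test of change, not to the mixed model as written. A class intercept that is constant over time cancels from a change score when data are balanced, so the written model may not protect the group-by-time contrast even at class level. That is a separate question. The 5% in the one-class-per-school row should not be read as the error rate of the written model.

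None of this supplies what is missing: a school term, a count of schools, or a limit on classes per school.

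**Conclusion.** The omission is real in both the model and the sample size; its consequence is conditional. If any school supplies two or more classes and changes vary between schools, the true standard error is about 3% to 19% above the planned one in the layouts examined. A nominal 5% class-level test then rejects about 5.7% to 6.6% of the time with one doubled school per arm, 6.3% to 7.7% with the control arm alone on four schools, and 7.6% to 10.7% with both arms on four schools. These figures assume the stated layouts and that half or all of the 0.04 lies at school level. If each school supplies one class, school and class coincide and the school layer changes nothing.

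A reader might infer that the trial will run at a type I error near 10%, or that classes are known to share schools. The documents support neither. This is a cheap improvement to make before data collection, not a demonstrated error in the result.

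**What to change.** - Put a school code on each questionnaire box and carry it into the data set. The documents describe only a child ID, and the name envelopes stay at school to be destroyed, so the link could be hard to rebuild later.
- If any school supplies more than one class, make school the top cluster for the group-by-time contrast, through a school-by-time random term or an analysis of change at school level. A school intercept alone is not enough, because it cancels from change. Use small-sample degrees of freedom based on the number of schools.
- In 1.6, state the number of schools per arm. If it is below seven, restate the detectable difference on those degrees of freedom: for example about 0.137 to 0.148 with four schools per arm, against about 0.113 on 12 df with one class per school.

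The cost is a code on each box and one model term. When schools supply several classes, there are fewer degrees of freedom and the stated detectable difference is larger. Separate school and class variances may be weakly estimated from so few schools; in that case use the school-level analysis alone.
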